## **Ethics**

Akdeniz University Medical Faculty Clinical Research Ethics Committee has approved the trial (reference number: 2015/399), with anonymized results to be released in ClinicalTrials.gov. All patient will be provided with trial information, with all patients wishing to participate in the trial providing informed consent, which included an agreement for the use of anonymised data for research, before commencing treatment.

All treatment procedures and medical devices used in treatments have been approved by the Turkish Health Ministry and the management and quality control of the procedures performed accredited by TÜV Rheinland Cert GmbH (Assisted Reproductive Technologies; ISO 9001:2008; Cert No. 01 100 062424).

## **Data**

All data pertaining to the trial and required for analysis will be collected by the principal investigator from the IVF database of Antalya IVF at >20 weeks after the last patient randomized had

undergone FET. A LB cycle will defined as a pregnancy cycle delivered at >20 weeks of gestation. A clinical pregnancy will defined as a pregnancy cycle with a fetal sac observed on ultrasound at >5 weeks of gestation. A miscarriage will be defined as a clinical pregnancy lost at <20 weeks of gestation.

**Figure 1:** Study design

Eligible patients		Enrollment	Inclusion criteria:
			Own oocytes; normo-ovulatory; $\leq 35$ years of age; $\leq 3$ embryo transfers; $\geq 18$ - $\leq 35$ kg/m  BMI; $\geq 5$ AFC. Informed consent
Assessment:		Randomization	Exclusion:
			No oocytes retrieved; $< 2$ blastocysts with morphological grade of $\geq 2$ BB
Assessment:			
			All blastocysts assessed morphologically
PGT group  1 blastocysts with morphological grade of $\geq 2$ BB biopsied and assessed by NGS	All blastocysts with morphological grade of $\geq 2$ BB cryopreserved	Morphology group	All blastocysts with morphological grade of $\geq 2$ BB cryopreserved
aneuploid blastocyst	euploid blastocyst		
Aneuploid subgroup: transfer of morphologically assessed blastocyst  Positive $\beta$ hCG 9 days of transfer	Euploid subgroup: transfer of a euploid blastocyst  Positive $\beta$ hCG 9 days of transfer	Morphology group: transfer of a morphologically assessed blastocyst  Positive $\beta$ hCG 9 days of transfer	

Fetal sac on ultrasound >5 weeks	Fetal sac on ultrasound >5 weeks	Secondary outcome measure	Fetal sac on ultrasound >5 weeks
--	--	----------------------------------	--

Live birth: Delivery at >20 weeks	Live birth: Delivery at >20 weeks	Primary outcome measure	Live birth: Delivery at >20 weeks
---	---	--------------------------------	---

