**Changes to original registration:**

**Primary outcome measure:** the primary outcome measure was changed from ongoing pregnancy (i.e., clinical pregnancy at  $>14$  weeks of gestation) to the preferred outcome of live birth (LB, a delivery at  $>20$  weeks, with a live infant).

The AFC cut-off was changed to  $\geq 5$  (changed from  $\geq 10$ ) to be in line with the definition of decreased ovarian reserve and increase the eligible population.

**Trial registration:** ClinicalTrials.gov ID: NCT03095053

Protocol submission: 23 March 2017

Protocol revised submission: 28 March 2017

Randomized Controlled Trial registered and posted: 29 March 2017

Data collection start: 21 February 2018

Data collection was commenced at  $>20$  weeks from the date of last patient randomized had undergone FET

Data analysis start: 25 April 2018

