## Secondary objectives

The secondary objective of the RCT will be to investigate whether euploid blastocyst transfer results in reduced miscarriage, with a miscarriage defined as a clinical pregnancy lost at <20 weeks of gestation.

**Keywords:** blastocyst; comprehensive chromosome screening; euploidy; frozen embryo transfer

**Funding:** This RCT will not receive any specific grant from funding agencies in the public, commercial, or not-for-profit sectors, and therefore will be wholly funded by centre running the trial.

**Declaration of Interests:** The authors declare no conflicts of interest.

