## **Randomisation**

Patient couples who satisfy the inclusion criteria and who completed an informed consent will randomized by computer generated number in a 1:1 ratio on day 5 of in vitro embryo culture to the two arms, with the FET drug prescription indicating allocation to the ***the PGT group***, in which all blastocysts will be assessed according to standard morphological parameters, with the best scoring blastocyst to undergo biopsy and PGT for aneuploidy or ***the morphology group***, in which all blastocysts will be assessed according to standard morphological parameters, with the best scoring blastocyst selected for transfer (figure 1). Patient couples in the PGT group will be subgrouped

according to whether the blastocyst biopsied is predicted to be euploid (**the euploid subgroup**) or aneuploid (**the aneuploid subgroup**). In the aneuploid group the next best morphology scoring blastocyst will be transferred.

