## **Outcome measures**

Patient variables recorded will be maternal age, infertility duration and etiology, BMI, AFC, and endometrial thickness. The treatment cycle variables recorded were oocyte number, mature oocyte number, blastocyst number (i.e., the number usable blastocysts, with grade  $\geq 2$ BB), oocyte maturity, oocyte fertilization, blastocyst rate (i.e., the ratio of the number of blastocysts to the number of 2PN zygotes). The primary outcome measure recorded will be LB (changed from ongoing pregnancy),

with clinical pregnancy and miscarriage as secondary outcomes. A LB cycle will be defined as a pregnancy cycle that delivered at >20 weeks of gestation, resulting in a live infant. A clinical pregnancy will be defined as a cycle with a fetal sac observed on ultrasound after 5 weeks of gestation. A biochemical pregnancy will be defined as a cycle with an arbitrary serum  $\beta$ hCG concentration of >29 IU/L. Pregnancy tests will be performed 9 days after the FET.

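### The data-collection rule (more than 20 weeks after the last transfer, about 22w5d of gestation) does not ensure that live birth, the primary outcome, is known for the later transfers

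*Combined protocol and SAP*

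**What the plan says.** The Data section has the principal investigator take all data required for the analysis from the centre's database "at >20 weeks after the last patient randomized had" undergone FET. The section headed Changes to original registration reports the same timing as history: collection began more than 20 "weeks from the date of last patient randomized had undergone FET". That section also gives two dates: "Data collection start: 21 February 2018" and "Data analysis start: 25 April 2018". It does not give the date of the last FET.

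The primary outcome was changed from ongoing pregnancy to live birth. Outcome measures defines a live-birth cycle as one that "delivered at >20 weeks of gestation, resulting in a live infant". The Data section and Figure 1 omit the live infant from their wording but still require a delivery. The secondary outcomes are clinical pregnancy (a fetal sac on ultrasound after 5 weeks) and miscarriage, with "a miscarriage defined as a clinical pregnancy lost at <20 weeks of gestation".

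No section supplied for this review requires follow-up to delivery, sets a later lock for live birth, or says how a pregnancy still undelivered at analysis is counted. The Statistics section names p values and risk ratios and has no rule for missing outcomes.

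**The concern.** The collection rule is timed from transfer and has no delivery condition, while the primary outcome cannot be scored until delivery. An extraction that follows the rule exactly could therefore include women who are still pregnant, and the plan does not say what becomes of them.

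There are four ways to handle such a pregnancy:
- **Count it as a live birth.** This breaches the Outcome measures definition and in effect makes the endpoint ongoing pregnancy under a live-birth label.
- **Count it as not a live birth.** Both live-birth rates come out too low and precision falls.
- **Drop it.** Both rates again come out too low, because only successes-in-waiting are removed.
- **Query the database again after delivery.** This resolves the matter, but the plan does not provide for it.

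**Working it through.** The plan shows no calculation behind the 20-week figure, so there is nothing to reproduce. The check is date arithmetic.

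**1. Gestational age at transfer.** Progesterone starts on day 15 of preparation and transfer is on the 6th progesterone day (Frozen embryo transfer section): (15 − 1) + (6 − 1) = 19 days = 2w5d. Conventional dating of a day-5 blastocyst gives the same: 14 + 5 = 19.

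**2. Gestational age at the earliest permitted collection.** 19 + 140 = 159 days = 22w5d.
- To 37 weeks: 259 − 159 = 100 days = 14w2d.
- To 40 weeks: 280 − 159 = 121 days = 17w2d.
- Miscarriage is settled at 20 weeks: 140 − 19 = 121 days after FET, which is 19 days before the earliest collection. The rule therefore covers the secondary outcomes.

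The 37- and 40-week marks are assumptions; the documents give no gestation at delivery.

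**3. What the recorded dates allow.**
- Latest last FET: 21 February 2018 − 140 days = 4 October 2017 (one day earlier if more than 20 weeks is read strictly).
- From 4 October 2017 to analysis start on 25 April 2018 is 203 days; 203 + 19 = 222 days = 31w5d.
- To be at 37 weeks by analysis start, FET must be at least 259 − 19 = 240 days earlier: by 28 August 2017.
- To be at 40 weeks, 280 − 19 = 261 days earlier: by 7 August 2017. Reaching 40 weeks is still not delivery.

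**4. Effect on the risk ratio.** Let *p* be an arm's true rate and *f* the share of its ongoing pregnancies still undelivered, equal in both arms. For simplicity, treat every ongoing pregnancy as a future live birth.
- Counted as not live births: *p*₁(1 − *f*) / [*p*₂(1 − *f*)] = *p*₁/*p*₂. The ratio is unchanged. With unequal shares it is multiplied by (1 − *f*₁)/(1 − *f*₂).
- Dropped: each rate becomes *p*(1 − *f*)/(1 − *pf*).

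To illustrate, I use the centre's 66% and 52% from Sample size calculation. These are rates for euploid transfers and for morphology-selected transfers, not for the randomised arms. I also assume even accrual of transfers from mid-April or mid-May 2017 to 4 October 2017, with no delivery before 37 weeks. Then *f* = 37/172 = 21.5% or 37/142 = 26.1%.
- True ratio, and ratio if counted as not live births: 0.66/0.52 = 1.27.
- Ratio if dropped: 0.6037/0.4595 = 1.31 at *f* = 21.5%; 0.5894/0.4448 = 1.33 at *f* = 26.1%.
- Precision if counted as not live births: with equal arms, the variance of the log risk ratio is proportional to (1 − *p*₁)/*p*₁ + (1 − *p*₂)/*p*₂. This is 0.515 + 0.923 = 1.438 with full follow-up, 0.930 + 1.450 = 2.380 at *f* = 21.5%, and 1.049 + 1.601 = 2.650 at *f* = 26.1%. The standard error rises by a factor √(2.380/1.438) = 1.29 to √(2.650/1.438) = 1.36.

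This is the bounding case. With a last FET on 15 September 2017, *f* falls to 18/153 = 11.8% or 18/123 = 14.6%. With a last FET by 28 August 2017 it is zero on the 37-week mark.

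**The case against.** The strongest reply is that more than 20 weeks is a minimum. The history says only that collection commenced then, and neither the start of collection nor the start of analysis is a database lock. Analysis may have begun with baseline characteristics, and the centre could query its own database again. All of that stands. A reader might infer that live births were analysed before the women had delivered. The documents do not support this: the last FET date is not given, and a last FET by 28 August 2017 fits the record as well as one in early October.

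A reader might also infer that the treatment effect would be biased. Counting undelivered pregnancies as failures does shrink the absolute difference, by the factor 1 − *f*. But the plan names the risk ratio, which does not move when both arms are equally affected, and the documents give no reason to expect an imbalance. Nor is 66% against 52% the contrast between the randomised arms, because in the PGT arm "In the aneuploid group the next best morphology scoring blastocyst will be transferred". Those rates serve here only to illustrate the ratio.

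It is also tempting to say that the timing was left over from the earlier ongoing-pregnancy endpoint. That is plausible, but the documents do not say so and the point does not need it.

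What the reply does not answer is the rule itself. A minimum that permits extraction about 14 weeks before 37 weeks does not secure a delivery outcome, and the plan has no later step that does.

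**Conclusion.** The point holds as a gap between the collection rule and the primary outcome, not as evidence of missing data. As written, the rule can be met at 22w5d, some 14 to 17 weeks before term on the assumed 37- to 40-week marks. The recorded dates permit a last pregnancy at 31w5d when analysis started.

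If pregnancies were undelivered and counted as failures, the damage would be understated live-birth rates and lost precision (a standard error 29% to 36% larger in the bounding illustration). The risk ratio would be unchanged given equal shares in the arms. Dropping them would move it little (1.27 to at most 1.33 in the same illustration). Counting them as live births would change what the endpoint measures. The 22w5d figure rests on the protocol's own schedule; the illustrative figures rest on the stated accrual and delivery assumptions.

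**What to change.** In the Data section, replace the timing rule with: *Live birth data will be locked and analysed only when every pregnancy from a first FET has ended, at the latest about 40 weeks after the last FET.* The outer limit corresponds to 280 + 19 = 299 days = 42w5d of gestation, so it does not treat reaching 40 weeks as delivery. Add one sentence on how a pregnancy with an unknown delivery outcome is counted.

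If data were extracted while any pregnancy was ongoing, query delivery date and live-infant status again before the live-birth analysis. If that is not done, report the outcome as ongoing pregnancy past 20 weeks, not as live birth.

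The cost is one repeat database query and some delay. In the latest compliant case, 4 October 2017 + 280 days = 11 July 2018, which is 77 days or 11 weeks after the stated analysis start. With a last FET by 19 July 2017 (25 April 2018 − 280 days) there is no delay. No extra patients or procedures are needed.

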## Objectives

The primary objective of this RCT will be to investigate whether PGT for aneuploidy as a blastocyst selection method is superior to standard morphology scoring blastocyst selection, comparing the reproductive outcomes in FET cycles. The decision to transfer all blastocysts in FET will eliminate any potential impact of ovarian stimulation confounding on endometrial receptivity and to use freeze-all cycles will allow the use of the primary blastocysts of blastocyst cohorts. The primary outcome measure of this trial will be LB, with a LB defined as a pregnancy cycle delivering at >20 weeks of gestation.

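### The primary outcome has two wordings: Outcome measures requires a live infant, while Objectives, Data and Figure 1 require only delivery after 20 weeks

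*Combined protocol and SAP*

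**What the plan says.** Live birth (LB) is defined or described in five places in the combined protocol and SAP.

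- **Changes to original registration**, which announces the new primary outcome, asks for a delivery at more than 20 "weeks, with a live infant".
- **Outcome measures**: "A LB cycle will be defined as a pregnancy cycle that delivered at >20 weeks of gestation, resulting in a live infant".
- **Objectives**: "with a LB defined as a pregnancy cycle delivering at >20 weeks of gestation".
- **Data**: "A LB cycle will defined as a pregnancy cycle delivered at >20 weeks of gestation".
- **Figure 1**, all three columns, under the label of live birth: "Delivery at >20 weeks".

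Miscarriage, a secondary outcome, has a single definition. Secondary objectives gives it as "with a miscarriage defined as a clinical pregnancy lost at <20 weeks of gestation", and the Data section repeats it: "A miscarriage will be defined as a clinical pregnancy lost at <20 weeks of gestation".

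The Data section also fixes when outcomes are taken from the clinic database: "at >20 weeks after the last patient randomized had" undergone FET.

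**The concern.** A superiority trial needs one rule for its primary endpoint. Here the live-infant condition is present in two places and absent in three, and no sentence says which wording governs. The shorter wording appears in the statement of the primary objective and in the section on data collection, so it is not confined to a marginal part of the plan.

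The two rules disagree on one kind of event: a delivery after 20 weeks without a live infant. Under the shorter rule it meets the definition of the primary outcome. It cannot be recorded as a miscarriage either, because that category stops before 20 weeks, so it would not appear as a failure in any listed outcome. Two people coding the same records, each following a section of the plan, could report different primary counts. Following every pregnancy to term would not cure this, because the fault lies in the definition.

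**Working it through.** The plan states no figure that depends on this point, so there is none to reproduce. The check compares the wordings and then asks how many outcomes could be affected.

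**Step 1. Apply each wording to each event.**

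| Event | Outcome measures; Changes to original registration | Objectives; Data; Figure 1 | Miscarriage definition |
|---|---|---|---|
| Live infant delivered after 20 weeks | LB | LB | no |
| Delivery after 20 weeks, no live infant | not LB | **LB on the literal wording** | no |
| Clinical pregnancy lost before 20 weeks | not LB | not LB | yes |
| Loss at exactly 20 weeks | not LB | not LB | no |

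Only the second row separates the two rules. The fourth row is a gap in the secondary outcome alone: a loss at exactly 20 weeks is a primary-outcome failure under either rule.

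**Step 2. Expected number of outcomes scored differently.**

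Inputs:
- *n* = 74 (Sample size calculation). The section does not say whether this is per arm or in total; per arm is assumed.
- Planning rates of 66% and 52% (same section). These are ongoing-pregnancy rates for euploid and morphology-selected transfers, used here as upper bounds on deliveries after 20 weeks.
- *f*, the share of deliveries after 20 weeks without a live infant. The documents give no value; 0.5% to 3% is assumed.

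Formula: outcomes affected = *n* × rate × *f*.

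| *f* | 66% arm | 52% arm | Difference |
|---|---|---|---|
| 0.5% | 74 × 0.66 × 0.005 = 0.24 | 74 × 0.52 × 0.005 = 0.19 | 0.05 |
| 1% | 0.49 | 0.38 | 0.10 |
| 2% | 0.98 | 0.77 | 0.21 |
| 3% | 1.47 | 1.15 | 0.31 |

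So the expected number is one or fewer per arm up to *f* = 2%, and about 1.5 and 1.2 at the top of the range. If 74 is the total (37 per arm), the counts halve, to at most 37 × 0.66 × 0.03 = 0.73 and 37 × 0.52 × 0.03 = 0.58.

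**Step 3. Effect on rates and power.**

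One reclassified outcome moves an arm's rate by 1/74 = 1.35 percentage points. With 74 per arm, a two-sided 0.05 test and 72% against 52% (the plan's 20-point difference added to its 52%), power is 71%. Multiplying both rates by (1 − *f*) leaves it at 71% for *f* = 0.5% and lowers it to 68% for *f* = 3%.

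**Step 4. Can one event decide significance?**

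Uncorrected chi-square tests, 74 per arm:
- 48/74 v 36/74: p = 0.046
- 48/74 v 37/74 (one success added to the second arm): p = 0.067
- 49/74 v 37/74 (one added to each arm): p = 0.046

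A single event can cross the plan's 0.05 threshold, but only when the result already sits at the edge and the event falls in one arm alone. This example was chosen at the edge and does not predict what will happen.

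**Step 5. Can infant status be known when the data are extracted?**

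Counting a day-5 blastocyst transfer as 2 weeks 5 days of gestation (a convention, assumed here), 20 weeks after FET is 140 + 19 = 159 days, or 22 weeks 5 days. At that minimum interval the last patients' ongoing pregnancies would mostly be undelivered, so a live infant could not yet be confirmed for them.

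**The case against.** The strongest reply is that the intent is clear. The section whose task is to define outcomes requires a live infant, the notice of the changed primary outcome does too, and the term being defined is itself live birth. The shorter versions can be read as abbreviations that add a gestational threshold to a term that already says live. The Data section does not claim to override Outcome measures. This stands as far as intent goes. It does not remove the conflict, because three places give a complete definition without the condition and nothing ranks them.

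Two stronger readings are tempting, and neither is supported.

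- A reader might infer that stillbirths were counted as successes. The documents show only that the shorter wording permits it. No sentence says that a stillbirth or termination counts as a live birth.
- A reader might infer a bias favouring the morphology arm, because late losses could be commoner when ploidy is unknown. The documents give no late-loss or termination rate for either arm. The PGT arm also includes transfers of untested blastocysts: under Randomisation, only the best-scoring blastocyst is biopsied, and if it is aneuploid the next best by morphology is transferred. The direction of any bias cannot be established.

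It is also fair to object that the p-value example in the working is a knife-edge, and that the gap at exactly 20 weeks does not touch the primary outcome. Both objections stand.

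**Conclusion.** The inconsistency is real and lies in the current text. It concerns the primary endpoint: followed literally, the wording in Objectives, Data and Figure 1 would score a stillbirth after 20 weeks as a live birth, and the miscarriage definition would not pick it up. The text comparison needs no assumption.

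The size does need assumptions. With 74 per arm, the planning rates as upper bounds and 0.5% to 3% of deliveries after 20 weeks without a live infant, about 0.2 to 1.5 outcomes per arm would be scored differently, and one or fewer over most of that range. The expected difference between arms is at most about 0.3 of an outcome if the share is the same in both. No figure stated in the plan changes. The correction is warranted because the primary count should not depend on which section is followed, and because the plan already contains the right wording. A large numerical effect is not expected.

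**What to change.** 1. Use the Outcome measures definition (delivery after 20 weeks resulting in a live infant) in Objectives, in Data and in all three columns of Figure 1.
2. State that any delivery or loss after 20 weeks without a live infant is a primary-outcome failure, and tabulate these events by arm.
3. Confirm infant status from delivery outcomes, and hold the final data extraction until the last pregnancies have delivered.
4. As a minor tidy-up of the secondary outcome only, assign losses at exactly 20 weeks to a category, for example by extending the loss category to 20 weeks inclusive.

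The cost is wording in three places, one added scoring rule, a check of infant status in the delivery outcomes, and a later extraction for the last patients. No extra patients or procedures are needed. The observed live-birth rate may be very slightly lower.
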